3.2.2.1.1 Haematology profile

The haematology profile (automated complete blood count) is one of the most commonly performed laboratory studies in clinical practice to evaluate the general health of a subject. Elevated or low measurements may indicate certain deficiencies, metals exposure, or other conditions. Specifically, we will examine the following: haemoglobin (Hb), white blood cell (WBC) count, red blood cell (RBC) count, haematocrit (Hct), mean cell volume of red cells (MCV), mean cell haemoglobin concentration (MCHC) of red cells, platelet (PLT) count, red cell distribution width (RDW), mean platelet volume (MPV), and differential leukocyte count (DLC).

3.2.2.1.2 Urinalysis

Urine removes toxins and excess liquid from the body and can therefore contain important clues regarding a person's general health and exposure to contaminants.

Urinalysis can be used to detect certain types of disease, particularly in the case of metabolic disorders and kidney disease. Urinalysis will include macroscopic examination (test strips) for: blood (Hb, erythrocytes), leukocytes, protein, pH, nitrite, and glucose for all the residents tested. Microscopic examination of urine sediment will be performed if there is a positive macroscopic result for blood, leukocytes protein (greater than trace), or if the glucose concentration is greater than 55 millimicromolars (nmol/l).

3.2.2.1.3 Blood biochemistry

Blood biochemistry tests can be indicative of the efficacy of various organ systems. These tests will examine bilirubin, creatinine, plasma cotinine, blood urea nitrogen (BUN), serum thyroid stimulating hormone (TSH), and free thyroxine 4 (fT4) concentrations as well as. Bilirubin is a yellow-orange pigment produced when the liver processes waste products. Excess levels in the blood produce the yellow appearance observed in jaundice and are thus indicative of liver function. Creatinine is a waste product of protein metabolism. Elevations in creatinine levels can be used to measure overall kidney function. Plasma cotinine is a breakdown product of nicotine and is widely used to verify recent exposure to cigarette smoke. TSH leads to the production and release of thyroid hormones, fT4 being one of the most important, and is responsible for regulating general growth and metabolism. Serum TSH and fT4 measurement is an important test for many aspects of pituitary and thyroid function. BUN is a measure primarily of the levels of urea (cleared by the kidney) in blood. Therefore, conditions associated with compromised kidney function frequently lead to increased levels of urea in the blood.

3.2.2.2 Metal tests

The four CoCs, nickel, copper, cobalt, and arsenic can be detected in urine following ingestion or inhalation exposure. It is possible that a relationship may exist between concentrations of these metals in urine samples and the environmental concentrations to which subjects have been exposed. In addition, it is possible that the data from these analyses may provide a better understanding of the relationship between the CoCs and the residents' health status.

In addition to measurements of CoCs levels in urine, mercury, lead and cadmium levels will be assessed in urine and blood, respectively. These non-CoCs tests are elaborated upon in the section 4.3.5, under Confounders.

3.2.2.3 Non-Specimen related tests and data points

This series of tests and measures is designed to provide critical health information not generated by the specimen-related tests. Non-specimen related tests and data points include a lung function test, skin sensitivity assessment, electrocardiogram (ECG), blood pressure measurement, carbon monoxide (CO) breath test, and general measures (eg. height and weight).

3.2.2.3.1 Lung function

The lung function test will assess lung volume and forced ventilatory flows. The following three tests will be used to measure each subject's ability to move air rapidly in

and out of the lungs: 1) FVC (forced vital capacity), the volume of gas delivered during an expiration made as forcefully and completely as possible starting from full inspiration; 2) FEV1 (forced expiratory volume in 1 second), the volume of gas exhaled in one second from the start of the FVC maneuver and; 3) PEF (peak expiratory flow rate), the maximal flow during an FEV maneuver starting from a position of full inspiration. The specific ventilatory mechanics of the lungs are indicative of a number of pulmonary diseases (e.g. asthma, emphysema, obstructive air disease).

3.2.2.3.2 Skin sensitivity

Finally, skin sensitivity to nickel and cobalt also will be assessed. Long-term exposure to both nickel and cobalt contaminated dust has been shown to result in allergic sensitization leading to an increased incidence of allergic contact dermatitis. While primary allergic contact dermatitis has a good medical prognosis, continued exposure to the putative allergen may lead to chronic forms of dermatitis sites, such as the hands (Christensen, 1990; Schubert, 1990). Contact allergy is never inborn, although there may be some genetic factors that play a role in the development of the allergy (Menne and Neiboer, 1989). Following chronic exposure, sensitization to these metals can often occur, at which point the hypersensitivity is likely lifelong. Studies of the prevalence of delayed type hypersensitivity reactions/allergy to nickel in the general population have shown a prevalence range of 8% to 11% in females and 1% to 2% in males (Nielsen and Menne, 1993; Peltonen, 1979). More recently, considerably higher prevalence rates have been reported in the northern regions of Norway and Finland, namely, 27.5% to 39% of females (Smith-Sivertsen et al., 1999) and 5% of males (Smith-Sivertsen et al., 1999).

The prevalence of nickel allergy found in selected clinical populations referred for patch testing has shown a uniform prevalence of 14.3% (Marks et al., 1998, 1999, 2000, 2001) the prevalence for cobalt has been in the range of 6.8% to 9%. The marked difference between genders appears to be due to differences in the prevalence of ear piercing and the use of jewelry (Nielsen and Menne, 1993; Smith-Sivertsen et al., 1999; Smith Sivertsen et al., 2002). Based on the classification of both nickel and cobalt as CoCs and the clear relationship between chronic exposure to these metals and their dermatologic effects, the present study will include a skin patch test to assess sensitization to both nickel and cobalt.

3.2.2.3.3 Additional tests and general measures

Cardiovascular and circulatory issues will be assessed using the ECG and blood pressure tests. The ECG measures the electrical potential of the heart during contraction, while the blood pressure test will assess systolic and diastolic pressure. The CO breath test can be used to assess lung disease and to determine the exposure to smoke. In addition to these tests, general measures, such as height and weight, will be taken.

3.2.2.5 Validation

The individual medical tests described above have been included both for their utility in measuring general health and health conditions associated with exposure to the CoCs, as well as for purposes of validation. That is, specific medical tests also can be used as objective measures to validate reported medical health information from the health

questionnaire that is subjective in nature (Moffat et al., 2000; Smith- Sivertsen et al., 2000).

Medical tests that will serve as validators in this study include:

- Bilirubin test: validates the jaundice question in the questionnaire,
- Plasma cotinine test: validates recent smoking history question in the questionnaire,
- Serum TSH and fT4 test: validates thyroid condition questions in untreated individuals,
- ECG test: validates history of heart attack question in the health questionnaire,
- CO breath test: validates recent smoking history question in the health questionnaire,
- FEV1/FVC/PEFR tests: help to validate chronic bronchitis, emphysema, chronic obstructive pulmonary disease, asthma and other respiratory questions from the health questionnaire, and
- Skin patch tests: validates contact dermatitis question from the health questionnaire.

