In measuring any parameter of health, it needs to be noted that measurements need to be evaluated in reference to other measures in the body. An elevation of one parameter may seem to be an issue as it is out of range and yet when viewed holistically, the data can be normal for the age and gender. The data will all be viewed accordingly and any values that are of concern will be put into context both in the analysis and in communication with the subject and local physician. This is especially important when one considers that in general there is a background level of most metals and trace elements in everybody. The levels of CoCs found in the community of Port Colborne will be compared to standard reference ranges. In the analysis, the confounder data collected will be utilized to add context to the data. There may be instances where the very nature of the confounder will result in the fact that an outcome could be due to more than one cause. Confounders include, diet and food in general. Arsenic levels can be elevated by the ingestion of shellfish. This can be differentiated by utilizing a fractionated arsenic measure methodology that will identify organic and non-organic arsenic. The asthma symptoms and signs could be due to atopy (genetic susceptibility to allergies) in the subject, and therefore the person has hyperreactive airways to a number of airborne irritants. Hypersensitivity to nickel could be confounded by the level of jewelry that pierces the skin. Cobalt could be elevated due to the presence of a prosthesis device. This will all be clearly addressed during the review of each participants data and in the analysis. Other confounders that will be taken into account are lifestyle factors, such as smoking or use of alcohol. These are associated with many health risks including cancer and heart disease, use of prescription medications, OTC, Health supplements, such as those that contain vitamin B12 and other natural products. The use of medicinal products,

although treating one set of specific symptoms, may effect other haematological parameters. For example the use of Lithium can increase TSH levels, certain anti-inflammatory drugs can effect T-4 levels, codeine can effect liver enzyme levels.

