4.2.3.3.1 Skin sensitivity assessment

Prior to dermatology testing, subjects will have filled out the health questionnaire which contains dermatology questions that will be used to obtain information concerning dermatological points of interest including questions about jewelry that pierces the skin and the possible presence of atopic dermatitis. A standardized ready to use patch test system, the TRUE test, will be employed (Brasch et al 2001; Suneja and Belsito 2001). This system has been found to be at least as comparable in terms of accuracy and reproducibility, to the conventional Finn Chamber technique of patch testing in its detection of nickel and cobalt allergic individuals (Suneja 2001, Golhausen 1989).

A group of trained study nurses will perform all patch test administration, including application and removal. Patch test scoring will be carried out by a smaller group of specially trained study nurses to maintain high inter-rater reliability. Patch tests will be applied on the upper back. Their edges will be marked with a hypoallergenic marker. Patch tests will remain on the skin for a period of 48 ± 2 hours. During this time, subjects will be given written instructions on test compliance (see Appendix 11.3 for more information). Following this, patch tests will be removed by a trained nurse. Skin sensitivity will be scored 48 hours following removal of the patch test (at 96 hours).

Patch test responses will be scored as either negative, or positive. A positive patch test result is interpreted as a 1+, 2+ or 3+ reaction. This interpretation is based on the following scale (ICDRG 1984): a) 1+ = diffuse confluent erythema with palpable infiltration; b) 2+ = erythema and infiltration with papules and discrete vesicles; and c) 3+ = spreading strong erythema and infiltration with coalescing vesicles/bullous reaction and / or crust with ulceration. Irritant reactions (weak, macular erythema without infiltration or a follicular (pore) pattern restricted to the area covered by the patch) are not regarded as positive and are denoted as “IR”.

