28. In the past month, were you exposed to second-hand smoke on most days? 
- Yes (Go to Q29)
 - No (Go to Q29)
 - DK, R (Go to Q30)

29. Does smoke from cigarettes cause you any physical irritation (for example, to your eyes, your breathing, your throat)? 
- Yes (Go to Q30)
 - No (Go to Q30)

When we use the word drink it means:

- one bottle or can of beer or a glass of draft
- one glass of wine or a wine cooler
- one drink or cocktail with 1 and a 1/2 ounces of liquor.

30. During the past 12 months, have you had a drink of beer, wine, liquor or any other alcoholic beverage?  ADULT
- Yes (Go to Q31)
 - No (Go to Q34)
 - DK, R (Go to Q36)

31. During the past 12 months, how often did you drink alcoholic beverages?  (Go to Q32)
- Less than once a month
 - Once a month
 - 2 to 3 times a month
 - Once a week
 - 2 to 3 times a week
 - 4 to 6 times a week
 - Every day

32. How often in the past 12 months have you had 5 or more drinks on one occasion? 
(Go to Q33)

- Never
- Less than once a month
- Once a month
- 2 to 3 times a month
- Once a week
- More than once a week

33. Thinking back over the past week, did you have a drink of beer, wine, liquor or any other alcoholic beverage?  (Go to Q 36)

- Yes
- No
- DK, R

34. Have you ever had a drink? 

- Yes (Go to Q 35)
- No (Go to Q36)
- DK, R (Go to Q36)

35. Did you ever regularly drink more than 12 drinks a week? 

- Yes (Go to Q 36)
- No (Go to Q36)
- DK, R (Go to Q36)

Educational Information

36. Please fill in the following table regarding all of the schools you have attended in Port Colborne up to and including high school: CHILD

School Name	Town, Province	Duration of Stay at School (YYYY to YYYY)

Other Exposure Information

37. Do you wear, or have you ever worn jewelry that pierces the skin?

- Yes
- No
- Don't Know/Refused

38. How many individual piercings do you have?

39. Did you ever have a skin irritation that was relieved by removing the jewelry?

Yes

No

Don't Know/Refused

Health-Related Quality-of-Life Measure

1. Would you say that in general your health is:  

- a. Excellent
- b. Very Good
- c. Good
- d. Fair, or
- e. Poor?

2. Recent Physical Health 

Now thinking about your physical health, which includes physical illness and injury, for how many days during the past 30 days was your physical health not good?

_____ days

3. Recent Mental Health 

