- Rhinitis
- Nasal Polyps
- Nasal Septal Ulceration
- Other, Please specify

19. How old were you when this was first diagnosed?

_____ Age in years
(MIN: 0) (MAX: current age)

Skin:

20. Do you have a skin condition?

- Yes
- No (Go to Q23)
- Don't Know, Refused (Go to Q23)

21. What type of skin condition do you have:

INTERVIEWER: Mark all that apply.

- 1 Dermatitis/eczema
- 2 Pigmentation change (skin darkening or lightening; "change in skin color")
- 3 Hyperkeratosis (skin thickening)
- 4 Other, Please specify

22. How old were you when this was first diagnosed?

_____ Age in years
(MIN: 0) (MAX: current age)

Cardiovascular:

23. Do you have high blood pressure? 

- Yes
- No (Go to Q25)
- Don't Know, Refused (Go to Q25)

24. How old were you when this was first diagnosed? 

_____ Age in years
(MIN: 0) (MAX: current age)

Remember, we're interested in conditions diagnosed by a health professional.

25. Do you have migraine headaches? 

Yes

No (Go to Q27)

Don't Know, Refused (Go to Q27)

26. How old were you when this was first diagnosed? 

____ Age in years

(MIN: 0) (MAX: current age)

27. Do you have heart disease? 

Yes

No (Go to Q29)

Don't Know, Refused (Go to Q29)

28. How old were you when this was first diagnosed? 

____ Age in years

(MIN: 0) (MAX: current age)

29. Have you ever had a heart attack (damage to the heart muscle)? 

Yes

No (Go to Q30)

30. Do you currently have angina (chest pain, chest tightness)? 

Yes

No (Go to Q31)

31. Do you currently have congestive heart failure (inadequate heart beat, fluid build-up in the lungs or legs)? 

Yes

No (Go to Q32)

Thyroid:

32. Do you have a thyroid condition? 

Yes

No (Go to Q34)

DK, R (Go to Q34)

33. How old were you when this was first diagnosed? 

____ Age in years

(MIN: 0) (MAX: current age)

Gastro-intestinal/Liver:

34. Do you have stomach or intestinal ulcers? 

Yes

No (Go to Q36)

DK, R (Go to Q36)

35. How old were you when this was first diagnosed? 

____ Age in years

(MIN: 0) (MAX: current age)

36. Do you have Gastroenteritis?

Yes

No (Go to Q38)

DK, R (Go to Q38)

37. How old were you when this was first diagnosed?

____ Age in years

(MIN: 0) (MAX: current age)

38. Do you have Jaundice?

Yes

No (Go to Q40)

DK, R (Go to Q40)

39. How old were you when this was first diagnosed?

____ Age in years

(MIN: 0) (MAX: current age)

Neurological:

40. Do you have Peripheral Neuropathy (numbness or tingling in fingers or toes)?

Yes

No (Go to Q42)

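### The patch test is said to validate a contact dermatitis question, but the questionnaire has only one combined dermatitis/eczema option and cannot separate contact from other dermatitis

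*Protocol*

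**What the plan says.** - Section 3.2.2.5 (Validation) lists medical tests that serve as objective checks on self-reported answers. One entry reads: "Skin patch tests: validates contact dermatitis question from the health questionnaire".
- Section 4.2.3.3.1 (Skin sensitivity assessment) says that the questionnaire, completed before patch testing, contains "questions about jewelry that pierces the skin and the possible presence of atopic dermatitis".
- Appendix 10.1, Current Medical Health Status, Skin: Q20 asks "Do you have a skin condition", and a No skips to Q23. Q21 then offers four types, the first being "Dermatitis/eczema". Q22 takes a single age at diagnosis. The introduction to this part restricts answers to professionally diagnosed conditions lasting, or expected to last, six months or more.
- Appendix 10.1, Other Exposure, Q39: "Did you ever have a skin irritation that was relieved by removing the jewelry".
- Section 3.4 (Study Limitations), on alternative explanations: "Hypersensitivity to nickel could be confounded by the level of jewelry that pierces the skin". Atopy is raised there for a different outcome: "The asthma symptoms and signs could be due to atopy".
- Mock Table 11 (Section 6.5.1) compares patch results between areas with adjustment for age and sex only. Mock Table 6 has a Dermatitis row compared with Ontario.

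**The concern.** Two sections assign two different diagnoses to the questionnaire, and the instrument has one undifferentiated tick-box for both. A validation exercise needs a self-report and a test aimed at the same condition. Here the test detects sensitisation to nickel and cobalt, while the self-report covers contact, atopic and any other dermatitis.

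A woman with atopic eczema who answers truthfully will usually be patch-negative and will look like a misreporter. In the other direction, a sensitised person with no current long-term diagnosis answers No at Q20 and never reaches Q21. Section 3.2.2.3.2 describes the hypersensitivity as probably lifelong, so current symptoms and patch status need not coincide.

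A statistical analysis plan cannot repair this later, because an answer that was never collected cannot be split. There is also a secondary risk: the combined item might be taken as the atopy variable in a model for nickel sensitivity, although it includes dermatitis that nickel itself may have caused.

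**Working it through.** **Is there another item?** The full questionnaire is in Appendix 10.1. No item names contact dermatitis or atopic dermatitis. Q39 is the nearest. It sits among the exposure questions, asks about irritation rather than a diagnosis, and covers jewelry only, whereas Section 3.2.2.3.2 attributes sensitisation also to nickel- and cobalt-contaminated dust. It is a partial contact item.

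**How far would truthful answers agree with the patch test?** The protocol gives no figure to reproduce, so this is an illustration.

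Inputs:
- s = 9.5% of women nickel-sensitive (Section 6.1.1).
- c = share of sensitised women with contact dermatitis: assumed 30%, 50% or 70%.
- o = share of all women with other dermatitis or eczema: assumed 2%, 5%, 10% or 15%, independent of sensitisation.

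Share of women marking the option who are patch-positive:

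PPV = s[1 − (1 − c)(1 − o)] / {s[1 − (1 − c)(1 − o)] + (1 − s)o}

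Example with c = 50% and o = 10%: the numerator is 0.095 × (1 − 0.5 × 0.9) = 0.095 × 0.55 = 0.0523. The other term is 0.905 × 0.10 = 0.0905. PPV = 0.0523 / 0.1428 = 0.366.

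| o | c = 30% | c = 50% | c = 70% |
|---|---|---|---|
| 2% | 62% | 73% | 79% |
| 5% | 41% | 52% | 60% |
| 10% | 28% | 37% | 43% |
| 15% | 22% | 29% | 34% |

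A truthful item restricted to nickel contact dermatitis would give 100% under the same assumptions. Setting PPV = 0.5 gives o = sc / [(1 − s) − s(1 − c)]. Patch-negatives are therefore the majority once other dermatitis exceeds 3.4% (c = 30%), 5.5% (c = 50%) or 7.6% (c = 70%).

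**What if the item were entered as a covariate for patch positivity?** Inputs: baseline 9.5%, area odds ratio 2.2 (Section 6.1.1), equal area sizes, other dermatitis 5%, 10% or 15%, and a logistic model with area and the combined item. The dermatitis risks are assumed.

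| Dermatitis risk in the sensitised, unexposed → exposed | Extra dermatitis in exposed, non-sensitised | Adjusted OR at o = 5%, 10%, 15% |
|---|---|---|
| 30% → 30% | 0 | 2.20, 2.20, 2.20 |
| 30% → 50% | 0 | 1.93, 2.03, 2.08 |
| 30% → 70% | 0 | 1.56, 1.79, 1.90 |
| 50% → 70% | 0 | 1.80, 1.95, 2.02 |
| 50% → 90% | 0 | 1.28, 1.61, 1.78 |
| 50% → 50% | 5% | 1.80, 1.93, 2.00 |
| 30% → 70% | 5% | 1.34, 1.59, 1.74 |

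When exposure acts on dermatitis only through sensitisation, at constant risk, nothing changes. In the other 18 cases the odds ratio falls by 5% to 42%. In 14 of them the change exceeds 10%, the threshold at which Section 3.3 would retain the item as a confounder. The same section defines a confounder as something that does not result from the exposure, a condition this item may fail.

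**The case against.** A reader might infer that the protocol already plans the combined item as an atopy covariate for nickel sensitivity. The documents do not support that. Section 3.4 names piercing jewelry for nickel hypersensitivity and mentions atopy only for asthma. The covariates given as examples in Section 6.4 are age, sex, smoking, alcohol and socio-economic status. The patch-test mock tables adjust for age and sex only. The lists are open, so later use is possible, but it is not planned. Nor would adjustment remove the nickel effect: no case run did so, and one showed no change at all.

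It is also tempting to call the validation uninterpretable, or to say that most truthful answers would be patch-negative. Both go too far. Q39 gives a partial contact item, trained nurses conduct the interviews, and a cross-tabulation remains possible. Whether patch-negatives are the majority depends on rates that the protocol does not give. The requirement of a professional diagnosis lasting six months may push other dermatitis towards the low end. Counting cobalt reactions as well would raise agreement somewhat.

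Finally, validation is ancillary, since patch positivity is reported in its own right. That limits the weight of the point. What stands is that the named question does not exist, and that the available item confuses two explanations which the validation is meant to separate.

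**Conclusion.** The concern holds as a mismatch between Sections 3.2.2.5 and 4.2.3.3.1 and the questionnaire, and that much needs no assumed figure. Its consequence is that low agreement with the patch test could mean misreporting or true non-contact eczema, with no way to tell which. The illustrated agreement of 22% to 79% under fully truthful answers rests on assumed dermatitis rates, independence between the two kinds of dermatitis, and nickel alone. Only the 9.5% comes from the protocol.

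The adjustment point is conditional. If the item were used as an atopy covariate, attenuation could run from none (odds ratio 2.20) to substantial (1.28) under the scenarios above. It is a caution about possible use and does not describe a planned analysis.

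**What to change.** - Split option 1 of Q21 into contact or allergic dermatitis (for example from metal or jewelry) and other dermatitis or eczema.
- Add a separate item on ever having had atopic dermatitis or childhood eczema, outside the Q20 skip. Behind that gate, people whose eczema has resolved would be missed.
- In Section 3.2.2.5, name the new contact option together with Q39 as what the patch test validates. Note that contact dermatitis from non-metal causes can still be patch-negative.
- State that the combined item will not be used to adjust analyses of nickel or cobalt sensitivity.
- Recombine the two Q21 options for the Dermatitis row of mock Table 6.

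The cost is one or two extra questionnaire lines before pre-testing. Q20 to Q22 carry no source mark in the text as read, so the commitment in Section 4.2.2.1 not to reword borrowed items does not appear to be touched. The marks are icons that may not all have survived extraction, so the sponsor should confirm the source of these items first.
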